3.0 Patient Demographics and Baseline Characteristics

(1) Analysis set to be used

Safety analysis set

(2) Data to be analyzed

For each data item, patients will be stratified into the following categories, and the number and frequency of patients will be calculated:

Data item	Category
Sex	Male or female
Age	Summary statistics
	<18 years, 18 to 39 years, 40 to 64 years, 65 to 74 years, or ≥75 years
	<18 years, 18 to 64 years, 65 to 74 years, or ≥75 years
Disease duration	<1 year, <1 to 3 years, <3 to 5years, ≥5 years, or unknown
Diagnosis	Hodgkin's or anaplastic large-cell lymphoma or other
Status	Relapsed/refractory, or new-onset
CD30	Positive, negative, or not measured
Site(s) of involvement	Lymph node, spleen, liver, lung, bone, central nerve, bone marrow, skin, and/or other
ALK (for patients with anaplastic large-cell lymphoma)	Positive, negative, or unknown
Clinical stage	I, II, III, IV, or unknown
B symptoms	Absent or present
ECOG Performance Status	0, 1, 2, 3, or 4
Therapeutic category	Outpatient or inpatient
Hypersensitivity disposition	Absent, present, or unknown
Specific hypersensitivity disposition(s)	Medications, food allergy, and/or other
HCV antibody	Negative, positive, or unknown
HBs antigen	Negative, positive, or unknown
HBs antibody	Negative, positive, or unknown
HBV DNA	Negative, positive, or unknown
Past history of pulmonary disorders	Absent or present
Concurrent pulmonary disorders	Absent or present
Past history of	Absent or present

Data item	Category
malignant tumours	
Concurrent malignant tumours	Absent or present
Concurrent illness (other than pulmonary disorders and malignant tumours)	Absent or present
Specific concurrent illness(es) (other than pulmonary disorders and malignant tumours)	Diabetes mellitus, hypertension, dyslipidaemia, hyperuricaemia, hepatic disease(s), renal disease(s), infections, peripheral nerve disorders, and/or other
Past history (other than pulmonary disorders and malignant tumours)	Absent, present, or unknown
Weight	Summary statistics ----- <40 kg, <40 to 50 kg, <50 to 60 kg, <60 to 70 kg, ≥70 kg, or not measured
BMI	Summary statistics ----- <18.5, <18.5 to 25, <25 to 30, ≥30, or unknown
Smoking history	Never, current, past, or unknown
Prior drug therapy	Absent or present
Prior drug therapy regimen(s)	ABVD, CHOP, and/or other (If more than one drug therapies in the same category is used in the same patient, it will be counted as one patient.)
Number of prior drug therapy regimens	Summary statistics
Prior radiotherapy	Absent or present
Prior hematopoietic stem cell transplantation	Absent, present (autologous), or present (homologous)
Other prior therapies	Absent or present
Pregnancy during the observation period (for females only)	Absent or present

(3) Figure/table number

Table 3.0-1

4.0 Treatment Given

4.1 Treatment given

(1) Analysis set to be used

Safety analysis set

(2) Data to be analyzed

For each data item, patients will be stratified into the following categories, and the number and frequency of patients will be calculated:

Data item	Category
Initial dose of Adcetris	1.8 mg/kg or other
Mean dose of Adcetris	<1.8 mg/kg, 1.8 mg/kg, or ≥1.8 mg/kg
Dose of Adcetris per 3 weeks	<1.8 mg/kg, 1.8 mg/kg, or ≥1.8 mg/kg
Duration of treatment with Adcetris	1, 2, 3, 4, 5, 6, 7, 8, 9, 10, 11, 12, 13, 14, 15, or 16 cycles
Reason(s) for discontinuation of Adcetris	Treatment goal achieved, adverse event(s), lost to follow-up, transfer to another hospital, pregnancy, inadequate response, and/or other
Post-baseline hematopoietic stem cell transplantation	Absent or present
Type of post-baseline hematopoietic stem cell transplantation	Autologous or homologous
Drug(s) other than Adcetris used for the treatment of the primary disease	Absent or present
Drug(s) used for the prevention of infection	Absent or present
Specific drug(s) used for the prevention of infection	Antibiotics/synthetic antibacterial agents, antifungals, antivirals, trimethoprim-sulfamethoxazole combinations, and/or other prophylactics against infections

(3) Figure/table number

Table 4.1-1

4.2 Premedication to prevent infusion reaction

(1) Analysis set to be used

Safety analysis set

(2) Data to be analyzed

For each cycle, patients will be stratified into the following categories, and the number and frequency of patients will be calculated:

Data item	Category
Premedication to prevent infusion reaction	Absent or present
Specific premedication(s) used to prevent infusion reaction	Acetaminophen, antihistamines, and/or corticosteroids

(3) Figure/table number

Table 4.2-1

5.0 Safety Analysis

5.1 Occurrences of adverse events/infections and adverse drug reactions/infections

5.1.1 Occurrence of adverse events/infections

(1) Analysis set to be used

Safety analysis set

(2) Data to be analyzed

Data listed below will be analyzed.

For data entered in the field of “Adverse events: [1] Peripheral nerve disorders] in the case report form, MedDRA PT Code for peripheral sensory neuropathy, peripheral motor neuropathy, or peripheral neuropathy should be assigned, regardless of the LLT code entered in “Symptoms” field (see Section 1.1 “Definition;” the same applies hereinafter).

Neutropenia (PT Code 10029354) will be assigned to Neutrophil count decreased (LLT Code 10029366), Lymphopenia (PT Code 10025327) to Lymphocyte count decreased (LLT Code 10025256), Leukopenia (PT Code 10024384) to White blood cell count decreased (LLT Code 10047942), and Thrombocytopenia (PT Code 10043554) to Platelet count decreased (LLT Code 10035528) (the same applies hereinafter).

Data item	Data to be analyzed
Number of patients with adverse events, etc.	Number of patients experiencing adverse events, etc.
Number of adverse events, etc.	Number of adverse events, etc., observed. If the same patient has multiple occurrences of the same adverse event, etc. (PT), the total number of occurrences will be calculated.
Percentage of patients with adverse events, etc.	Is calculated using the following formula: number of patients with adverse events, etc./number of patients included in the safety analysis set × 100.
Type of adverse events, etc.	Adverse events, etc., will first be classified by SOC, within each of which adverse events, etc., will be further classified by PT. Laboratory test data will first be classified by SOC, and will then be grouped into each HLG and will be further classified by PT. For SOC, the number and percentage of patients with adverse events, etc., will be presented in the internationally agreed order. For PT, the number and percentage of adverse events, etc., will be presented in ascending order of PT codes. If the same patient has multiple occurrences of the same adverse event, etc. (PT), the event will be counted once per patient.

(3) Figure/table number

Table 5.1-1

5.1.2 Occurrence of adverse drug reactions/infections

(1) Analysis set to be used

Safety analysis set

(2) Data to be analyzed

Data listed below will be analyzed.

Data item	Data to be analyzed
Number of patients with adverse drug reactions, etc.	Number of patients experiencing adverse drug reactions, etc.
Number of adverse drug reactions, etc.	Number of adverse drug reactions, etc., observed. If the same patient has multiple occurrences of the same adverse drug reaction, etc. (PT), the total number of occurrences will be calculated.
Percentage of patients with adverse drug reactions, etc.	Is calculated using the following formula: number of patients with adverse drug reactions, etc./number of patients included in the safety analysis set × 100.
Type of adverse drug reactions, etc.	Adverse drug reactions, etc., will first be classified by SOC, within each of which adverse drug reactions, etc., will be further classified by PT. Laboratory test data will first be classified by SOC, and will then be grouped into each HLGT and will be further classified by PT. For SOC, the number and percentage of patients with adverse drug reactions, etc., will be presented in the internationally agreed order. For PT, the number and percentage of adverse drug reactions, etc., will be presented in ascending order of PT codes. If the same patient has multiple occurrences of the same adverse drug reaction, etc. (PT), the reaction will be counted once per patient.

(3) Figure/table number

Table 5.1-2

5.2 Seriousness, CTCAE Grade (the worst one), time of onset, time to the worst grade, and occurrences of adverse events/infections and adverse drug reactions/infections by outcome

5.2.1 Seriousness, CTCAE Grade (the worst one), time of onset, time to the worst grade, and occurrence of adverse events/infections by outcome

(1) Analysis set to be used

Safety analysis set

(2) Data to be analyzed

For each data item, patients will be stratified into the following categories, and the type of adverse events, etc., will be analyzed:

Data item	Category
-----------	----------

Seriousness	Serious or non-serious
CTCAE Grade (the worst one)	Grade 1, Grade 2, Grade 3, Grade 4, Grade 5, or unknown
Time of onset	1 to 7 days, 8 to 14 days, 15 to 21 days, 22 to 84 days, 85 to 168 days, 169 to 252 days, 253 to 336 days, or ≥ 337 days
Time to the worst grade	1 to 7 days, 8 to 14 days, 15 to 21 days, 22 to 84 days, 85 to 168 days, 169 to 252 days, 253 to 336 days, or ≥ 337 days
Outcome	Recovered/resolved, recovering/resolving, not recovered/not resolved, recovered/resolved with sequelae, died/fatal, or unknown

The type of adverse events, etc., will be analyzed as follows:

Data item	Data to be analyzed
Number of patients	Number of patients with adverse events, etc., by SOC/PT
Number of adverse events, etc.	Number of adverse events, etc., observed by SOC/PT
Type of adverse events, etc.	Adverse events, etc., will first be classified by SOC, within each of which adverse events, etc., will be further classified by PT. Laboratory test data will first be classified by SOC, and will then be grouped into each HLGT and will be further classified by PT. For SOC, data will be presented in the internationally agreed order. For PT, data will be presented in ascending order of PT codes. If the same patient has multiple occurrences of the same adverse event, etc. (PT), the total number of occurrences will be calculated per category (for example, if the same patient has one episode of serious diarrhea and one episode of non-serious diarrhea, these events will be counted once for each category).

(3) Figure/table number

Table 5.2-1

5.2.2 Occurrence of adverse events/infections by CTCAE Grade (the worst one)

(1) Analysis set to be used

Safety analysis set

(2) Data to be analyzed

For each data item, patients will be stratified into the following categories, and the type of adverse events, etc., will be analyzed:

Data item	Category
CTCAE Grade (the worst one)	\leq Grade 2, \geq Grade 3, or unknown

The type of adverse events, etc., will be analyzed as follows:

Data item	Data to be analyzed
Number of patients	Number of patients with adverse events, etc., by SOC/PT
Number of adverse events, etc.	Number of adverse events, etc., observed by SOC/PT
Type of adverse events, etc.	
Adverse events, etc., will first be classified by SOC, within each of which adverse events, etc., will be further classified by PT. Laboratory test data will first be classified by SOC, and will then be grouped into each HLGT and will be further classified by PT. For SOC, data will be presented in the internationally agreed order. For PT, data will be presented in ascending order of PT codes.
 
If the same patient has multiple occurrences of the same adverse event, etc. (PT), the event with the worst CTCAE grade will be counted once.

(3) Figure/table number

Table 5.2-2

5.2.3 Seriousness, CTCAE Grade (the worst one), time of onset, time to the worst grade, and occurrence of adverse drug reactions/infections by outcome

(1) Analysis set to be used

Safety analysis set

(2) Data to be analyzed

For each data item, patients will be stratified into the following categories, and the type of adverse drug reactions, etc., will be analyzed:

Data item	Category
Seriousness	Serious or non-serious
CTCAE Grade (the worst one)	Grade 1, Grade 2, Grade 3, Grade 4, Grade 5, or unknown
Time of onset	1 to 7 days, 8 to 14 days, 15 to 21 days, 22 to 84 days, 85 to 168 days, 169 to 252 days, 253 to 336 days, or ≥ 337 days
Time to the worst grade	1 to 7 days, 8 to 14 days, 15 to 21 days, 22 to 84 days, 85 to 168 days, 169 to 252 days, 253 to 336 days, or ≥ 337 days
Outcome	Recovered/resolved, recovering/resolving, not recovered/not resolved, recovered/resolved with sequelae, died/fatal, or unknown

The type of adverse drug reactions, etc., will be analyzed as follows:

Data item	Data to be analyzed
Number of patients	Number of patients with adverse drug reactions, etc., by SOC/PT
Number of adverse drug reactions, etc.	Number of adverse drug reactions, etc., observed by SOC/PT
Type of adverse drug reactions, etc.	
Adverse drug reactions, etc., will first be classified by SOC, within each of which adverse drug reactions, etc., will be further classified by PT. Laboratory test data will first be classified by SOC, and will then be grouped into each HLGT and will be further classified by PT. For SOC, data will be presented in the internationally agreed order. For PT, data will be presented in ascending order of PT codes.
 
If the same patient has multiple occurrences of the same adverse drug reaction, etc. (PT), the total number of occurrences will be calculated per category (for example, if the same patient has one episode of serious diarrhea and one episode of non-serious diarrhea, these adverse drug reactions will be counted once for each category).

(3) Figure/table number

Table 5.2-3

5.2.4 Occurrence of adverse drug reactions/infections by CTCAE Grade (the worst one)

- (1) Analysis set to be used

Safety analysis set

- (2) Data to be analyzed

For each data item, patients will be stratified into the following categories, and the type of adverse drug reactions, etc., will be analyzed:

Data item	Category
CTCAE Grade (the worst one)	≤Grade 2, ≥Grade 3, or unknown

The type of adverse drug reactions, etc., will be analyzed as follows:

Data item	Data to be analyzed
Number of patients	Number of patients with adverse drug reactions, etc., by SOC/PT
Number of adverse drug reactions, etc.	Number of adverse drug reactions, etc., observed by SOC/PT
Type of adverse drug reactions, etc.	Adverse drug reactions, etc., will first be classified by SOC, within each of which adverse drug reactions, etc., will be further classified by PT. Laboratory test data will first be classified by SOC, and will then be grouped into each HLGT and will be further classified by PT. For SOC, data will be presented in the internationally agreed order. For PT, data will be presented in ascending order of PT codes. If the same patient has multiple occurrences of the same adverse drug reaction, etc. (PT), the reaction with the worst CTCAE grade will be counted once.

- (3) Figure/table number

Table 5.2-4

5.3 Percentage of patients with adverse drug reactions/infections by patient demographics and baseline characteristics and treatment given

- (1) Analysis set to be used

Safety analysis set

- (2) Data to be analyzed

For each data item, patients will be stratified into the following categories, and the percentage of patients with adverse drug reactions, etc. (with point estimate and 95% confidence interval) will be determined.

For categories associated and not associated with ranking, Fisher’s exact and Mann-Whitney U tests, respectively, will be used.

Data item	Category
Sex	Male or female
Age	<18 years, 18 to 64 years, 65 to 74 years, or ≥ 75 years
Disease duration	<1 year, <1 to 3 years, <3 to 5 years, ≥ 5 years, or unknown
Diagnosis	Hodgkin's or anaplastic large-cell lymphoma or other
ALK (for patients with anaplastic large-cell lymphoma)	Positive, negative, or unknown
Clinical stage	I, II, III, IV, or unknown
B symptoms	Absent or present
ECOG Performance Status	0, 1, 2, 3, or 4
Hypersensitivity disposition	Absent, present, or unknown
Past history of pulmonary disorders	Absent or present
Concurrent pulmonary disorders	Absent or present
Past history of malignant tumours	Absent or present
Concurrent malignant tumours	Absent or present
Concurrent hepatic disorders	Absent or present
Concurrent renal disorders	Absent or present
Weight	<40 kg, <40 to 50 kg, <50 to 60 kg, <60 to 70 kg, ≥ 70 kg, or not measured
BMI	<18.5, <18.5 to 25, <25 to 30, ≥ 30 , or unknown
Smoking history	Never, current, past, or unknown
Prior drug therapy	Absent or present
Prior radiotherapy	Absent or present
Prior hematopoietic stem cell transplantation	Absent, present (autologous), or present (homologous)
Initial dose of Adcetris	1.8 mg/kg or other
Mean dose of Adcetris	<1.8 mg/kg, 1.8 mg/kg, or ≥ 1.8 mg/kg
Dose of Adcetris per 3 weeks	<1.8 mg/kg, 1.8 mg/kg, or ≥ 1.8 mg/kg
Drug(s) other than Adcetris used for the treatment of the primary disease	Absent or present

(3) Figure/table number

Table 5.3-1

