#### 7.4 Completion and submission of the case report form

For all patients requiring the completion of the case report form, the investigator will complete the case report form during the period from the start of treatment with Adcetris until the end of Cycle 4 and within 1 month after the end of Cycle 16, and submit it to the representative of Takeda.

If treatment with Adcetris is discontinued for any reason before the end of the observation period, the investigator will complete the case report form within 1 month after the completion of required observation submit it to the representative of Takeda. If treatment with Adcetris is discontinued due to any adverse event, however, the investigator will continue to observe the patient after treatment discontinuation until the adverse event resolves or improves wherever possible, and then complete the case report form and submit it to the representative of Takeda.

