## 9.1 Data to be recorded in Patient Enrollment Form

### 1) Outcome measures

Name of the institution, name of the investigator completing Patient Enrollment Form, expected date of the start of treatment with Adcetris, patient identification number, patient initial, sex, date of birth, diagnosis, performance status, CD30, past history of severe hypersensitivity to any ingredient of Adcetris, expected concomitant use of other antineoplastic drugs, and presence/absence of infections, peripheral nerve disorders, hepatic disorders, severe renal disorders, or pregnancy/breast-feeding

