### 9.2.3 Treatment given

#### 1) Outcome measures

Treatment with Adcetris and premedication to prevent infusion reaction (dose, date of premedication, and reasons for premedication to prevent infusion reaction and its discontinuation), (use or non-use, type, and date of) post-baseline hematopoietic stem cell transplantation, (presence/absence, name, and duration of) drugs other than Adcetris used for the treatment of the primary disease, and (presence/absence, name, and duration of) drugs used for the prevention of infection

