#### 2) When to collect outcome measure data

From the start of treatment with Adcetris until the completion of 16 cycles (or upon discontinuation of treatment with Adcetris)

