1.3 Level of significance and confidence coefficient

Level of significance: Two-sided 5%

Confidence coefficient: Two-sided 95%

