5.2.4 Occurrence of adverse drug reactions/infections by CTCAE Grade (the worst one)

(1) Analysis sets to be used

Safety analysis set, safety analysis set (Hodgkin’s lymphoma), and safety analysis set (anaplastic large-cell lymphoma)

(2) Data to be analyzed

For each data item, patients will be stratified into the following categories, and the type of adverse drug reactions, etc., will be analyzed:

Data item	Category
CTCAE Grade (the worst one)	≤Grade 2, ≥Grade 3, or unknown

The type of adverse drug reactions, etc., will be analyzed as follows:

Data item	Data to be analyzed
Type of adverse drug reactions, etc.	The incidence of adverse drug reactions, etc., for each CTCAE grade (the worst one) will be calculated by SOC and PT. For SOC, the number and percentage of patients with drug reactions, etc., will be calculated. For PT, the number and percentage of drug reactions, etc., will be calculated. SOCs will be presented in the internationally agreed order, and PTs will be presented in ascending order of HLGT and PT codes if their SOCs are “Investigations,” and in ascending order of PT code otherwise. The CTCAE grade (the worst one) is higher in the order of ≥Grade 3, ≤Grade 2, and unknown. If the same patient has multiple occurrences of the same adverse drug reaction, etc. (PT), the reaction with the highest CTCAE grade will be counted once per patient.

(3) Figure/table number

Tables 5.2.4-1 to 5.2.4-3

5.3 Percentage of patients with adverse drug reactions/infections by patient demographics and baseline characteristics and treatment given

(1) Analysis sets to be used

Safety analysis set, safety analysis set (Hodgkin’s lymphoma), and safety analysis set (anaplastic large-cell lymphoma)

(2) Data to be analyzed

For each data item, patients will be stratified into the following categories, and the percentage of patients with adverse drug reactions, etc. (with point estimate and 95% confidence interval) will be determined.

For categories associated and not associated with ranking, Fisher’s exact and Mann-Whitney U tests, respectively, will be used. If there is a category of “unknown,” it will be excluded to perform

the Mann-Whitney U test.

Data item	Category
Sex	Male or female
Age	<18 years, 18 to 64 years, 65 to 74 years, or ≥ 75 years
Disease duration	<1 year, <1 to 3 years, <3 to 5 years, ≥ 5 years, or unknown
ALK (for patients with anaplastic large-cell lymphoma)	Positive, negative, or unknown
Clinical stage	I, II, III, IV, or unknown

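### SAP 5.3 tests adverse drug reactions against an untimed, ever-used flag for other anti-lymphoma drugs, so the comparison is biased and its 5% error rate is not controlled

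*SAP*

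**What the plan says.** In the final-analysis SAP (the plan that fixes MedDRA 19.1 for the Final Survey Report), section 5.3 states that the "percentage of patients with adverse drug reactions, etc. (with point estimate and 95% confidence interval) will be determined" for each category of a list of factors. The last factor is "Drug(s) other than Adcetris used for the treatment of the primary disease", coded absent or present. The table is run in the whole safety set and separately for Hodgkin's lymphoma and anaplastic large-cell lymphoma. An older SAP version in the same file has the same row.

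For testing, Fisher's "exact and Mann-Whitney U tests, respectively, will be used". SAP 1.3 gives "Level of significance: Two-sided 5" percent.

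Protocol 9.2.3 records ("presence/absence, name, and duration of) drugs other than Adcetris used for the treatment of the primary disease". The collection period is "From the start of treatment with Adcetris until the completion of 16 cycles (or upon discontinuation of treatment with Adcetris"), and Protocol 9.2.5 gives adverse events the same period. Protocol 7.4 adds that, when Adcetris is stopped for an adverse event, "the investigator will continue to observe the patient after treatment discontinuation until the adverse event resolves or improves wherever possible". The enrolment form (Protocol 9.1) separately asks about "expected concomitant use of other antineoplastic drugs".

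**The concern.** The row treats something that accumulates during follow-up as if it were a baseline factor. Two routes can link it to reactions without any effect of the other drugs.

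- **Unequal observation.** The window ends at each patient's own discontinuation. A longer window gives more opportunity for a first reaction and more opportunity for an added drug.
- **Reverse order.** A patient who reacts in Cycle 2 and receives another drug in Cycle 6 is coded present, so the later drug is set against the reaction that preceded it.

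Protocol 10.4.2 names concomitant medication among the factors that may affect safety, and this row is its direct test for other anti-lymphoma drugs. A spurious finding that combination use raises reactions could reach the final report. The SAP does align exposure and event elsewhere: section 5.9.12 ties each infusion reaction to the most recent dose and uses doses as the denominator. Section 5.3 has no such rule.

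**Working it through.** **The plan's own figure.** The documents state no operating characteristic for the 5.3 test. The study size does reproduce: with an infusion-reaction frequency of 11% (Protocol 3.2), P(X ≥ 10 | n = 140) = 0.952, and 140 is the smallest n that reaches 0.95. The checks below use 140.

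**Mechanism by hand.** Assume a first-reaction probability of 0.15 per cycle, a drug-adding probability of 0.03 per cycle, the two independent, and no drug effect. Let half the patients be observed for 2 cycles and half for 14.

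- 2 cycles: P(reaction) = 1 − 0.85² = 0.278; P(use) = 1 − 0.97² = 0.059.
- 14 cycles: P(reaction) = 1 − 0.85¹⁴ = 0.897; P(use) = 1 − 0.97¹⁴ = 0.347.
- Reactions among users: (0.059 × 0.278 + 0.347 × 0.897) / (0.059 + 0.347) = 81%.
- Reactions among non-users: (0.941 × 0.278 + 0.653 × 0.897) / (0.941 + 0.653) = 53%.

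Within either window length, users and non-users have identical reaction rates. The 28-point gap comes entirely from pooling unequal windows.

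**Simulation, unequal windows.** 140 patients, up to 16 cycles, stopping probability 0.10 per cycle, no drug effect, Fisher's test at two-sided 5%, 2,000 simulated studies per cell. Assumed per-cycle probabilities are 0.05, 0.15, 0.40 and 0.60 for a first reaction (rows) and 0.01, 0.03 and 0.06 for adding a drug (columns). Entries are percentages of studies that reject.

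| Patients with any reaction | 8% use | 21% use | 36% use |
|---|---|---|---|
| 32% | 11 | 26 | 45 |
| 63% | 13 | 47 | 76 |
| 87% | 0.2 | 31 | 62 |
| 94% | 0 | 3 | 28 |

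Nearly all rejections point to more reactions among users (for example 78% v 59%). Between 18% and 80% of users had started the drug after their first reaction.

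**Other assumptions.**

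- Equal 16-cycle windows, independent drug starts: 0% to 4% with Fisher, 0% to 5% with Mann-Whitney. Later-started drugs are still counted here, yet there is no inflation.
- Front-loaded reactions (Cycle 1 risk 0.5 to 0.8, later 0.1 to 0.2, stopping 0.10): 0.4% to 38%.
- 30% of first reactions also end observation, drug-adding 0.03 to 0.06 per cycle: 14% to 46%.
- 10% of reacting patients go on to another recorded drug: 72%, 45% and 3% at any-reaction rates of 54%, 82% and 91%. With 20% doing so: 97%, 88% and 40%.

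**After correction.** With time-updated exposure (exposed only from drug start, log-rank score over cycles to first reaction), the rejection rate is 2% to 7% over the unequal-window and switching settings. A 2×2 table counting only drugs started by the cycle of the first reaction gives 1% to 6%. Its rejections lean towards apparent protection in most settings, because reaction-free patients have longer to become users. The time-updated form is therefore preferable.

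**The case against.** The best reply is that nothing in the documents shows the bias to be large.

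- Other-drug use may be rare. Protocol 9.2.5 speaks of pulmonary disorders in patients on Adcetris alone. At a drug-adding probability of 0.01 per cycle (5% to 8% use), with first-reaction probability 0.15 to 0.40 and stopping probability 0.10 to 0.18, rejection is only about 0.1% to 12%.
- The any-reaction rate may be near its ceiling. If independent, the five frequencies in Protocol 3.2 give 1 − 0.44 × 0.39 × 0.80 × 0.89 × 0.94 = 89% with at least one event (61% if fully overlapping). They are adverse events from non-Japanese studies, so they are only a guide. Near that ceiling with little other-drug use, the test falls below 5%.
- It is unclear whether a next-line drug started just after stopping Adcetris is recorded, since the collection period closes at discontinuation. Protocol 7.4 extends observation only after adverse-event discontinuations. The high switching figures depend on such drugs being captured.
- This is one of more than 20 unadjusted rows in a single-arm surveillance, with no decision rule attached.

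All of this stands as a limit on size and consequence. None of it supplies an ordering rule or an allowance for observation time.

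A reader might go further and infer that a false association is likely, or that counting drugs started after the reaction is enough to cause one. The documents do not support either. The rates needed for the first are absent, and the equal-window check contradicts the second. Nor is the direction guaranteed: if every reaction ended recording, the pull towards harm would vanish or slightly reverse.

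The test wording in 5.3 also appears to swap Fisher and Mann-Whitney between ranked and unranked factors. For a two-level factor this changes little.

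**Conclusion.** The concern holds as a matter of bias and uncontrolled type I error, not as a prediction of a false result. As written, the 5.3 row cannot be read as an effect of concomitant anti-lymphoma treatment. The main driver is the patient-specific window; reaction-driven change of therapy is a second route that the recording rules may narrow. Under the assumed rates with unequal windows, the false-positive rate runs from below 5% (little other-drug use, high reaction rate) to about 75%. Where the study would fall in that range cannot be determined from the documents, because use, any-reaction and stopping rates are not given.

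**What to change.** In SAP 5.3, replace the absent/present flag by time-updated exposure. A patient counts as exposed only from the start date of the other drug, and first reactions are counted per cycle, or per unit of patient-time at risk, up to first onset. The inputs are the recorded drug duration and the reaction onset date.

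The protocol lists duration rather than start date, and the case report form is not in the documents, so availability of start dates must be confirmed. If they are unavailable, show the row descriptively without a p-value.

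A flag for drugs already in use on the date of the first dose may be added as a secondary baseline factor. It should not replace the main analysis, because it would drop the later concomitant use that Protocol 10.4.2 asks about. The enrolment-form item records expected use, so it can only be a cross-check.

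The mean-dose and dose-per-3-weeks rows of 5.3 are also built after baseline and deserve the same look.

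The cost is a wording change, a little more programming, and a smaller exposed group or less exposed patient-time.
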